6.18 Pharmacodynamic Analyses

Biomarker analyses will be presented by treatment group for the PD Analysis Population per Table 1.

Table 1. PSC Biomarkers

Biomarker	Timepoints (Parts 1 and 2)	Timepoints (Part 3)
PRO-C3 [REDACTED]	Baseline, Weeks 2, 4, 8, 12 and Week 16 (off-treatment)	Baseline, Weeks 2, 4, 8, 12, 24, EOT (variable weeks) and EOS (variable weeks)
ELF [REDACTED]	Baseline, Weeks 4 and 12	Baseline, Weeks 4, 12 and 24
[REDACTED]	[REDACTED]	[REDACTED]
[REDACTED]	[REDACTED]	[REDACTED]
[REDACTED]	[REDACTED]	[REDACTED]
ALP, [REDACTED]	Baseline, Weeks 2, 4, 8, 12 and Week 16 (off-treatment)	Baseline, Weeks 2, 4, 8, 12, 18, 24, 32, 40, 48 and 52 (off treatment)

Biomarker results obtained from plasma, or serum samples will be summarized using descriptive statistics by treatment group and visit for each parameter. Actual biomarker concentration at each visit, the absolute change from baseline and relative change (percentage change) from baseline will be presented. [REDACTED]

[REDACTED]

Confidentiality Statement

This document [REDACTED] may not be duplicated, copied, altered or removed from company [REDACTED] without prior approval [REDACTED]

Controlled Quality Management Document

Sponsor:

Pliant Therapeutics Inc.

Protocol Number:

PLN-74809-PSC-203

STATISTICAL ANALYSIS PLAN

If provided, the result adjusted for dilution factor will be used in summaries and listings. Any samples hemolyzed, received ambient, or with a note indicating improper storage will be excluded from summaries and listed only. If a sample has been excluded, then the change from baseline for that sample will also not be calculated.

6.18.1 Biomarkers with One Post Baseline Assessment

The following endpoints include only one post baseline assessment for Parts 1, 2 and 3 Week 12 interim analysis:

Endpoints measured at baseline and only one post baseline visit will be analyzed by the analysis of covariance (ANCOVA).

The LS means, corresponding SEs, and 95% CI for each treatment group will be obtained from the model. An estimate for the LS mean difference (PLN-74809 vs. placebo), corresponding SE, 95% CI, and p-value for each dose group will also be presented. Each individual active group will be compared to pooled placebo (Parts 1, 2 and 3).

Actual biomarker concentrations will be presented as a box plot by treatment group for each parameter. In addition, line plots using the LS estimated values and corresponding SE will also be presented.

Confidentiality Statement

This document [REDACTED]
without prior approval

[REDACTED] may not be duplicated, copied, altered or removed from company [REDACTED]

Controlled Quality Management Document

Sponsor:

Pliant Therapeutics Inc.

Protocol Number:

PLN-74809-PSC-203

STATISTICAL ANALYSIS PLAN**6.18.2 Biomarkers with 2 or more Post Baseline Assessments**

The following endpoints include at least two post baseline assessments:

- Liver function parameters: ALP
- Liver fibrosis parameters: PRO

Endpoints measured at baseline and at least two post baseline visits will be analyzed using a mixed-effect model repeated measures (MMRM)

The LS means, corresponding SEs, and 95% CI for each treatment group at each visit will be obtained from the model. An estimate for the LS mean difference (PLN-74809 vs. placebo), corresponding SE, 95% CI, and p-value for each dose group at each visit will also be presented. Each individual active group will be compared to pooled placebo (Parts 1, 2 and 3).

Confidentiality Statement

This document [REDACTED] may not be duplicated, copied, altered or removed from company [REDACTED] without prior approval [REDACTED]

		Controlled Quality Management Document	
		Sponsor:	Pitant Therapeutics Inc.
		Protocol Number:	PLN-74809-PSC-203
STATISTICAL ANALYSIS PLAN			

[REDACTED]

[REDACTED]

[REDACTED]

[REDACTED]

For biomarkers with at least 2 postbaseline scheduled assessments, LS Mean change from baseline will be presented as a line plot showing baseline (0) and the LS mean (\pm SE) concentration at each post-dose visit by treatment group for each parameter.

[REDACTED]

[REDACTED]

[REDACTED]

[REDACTED]

[REDACTED]

[REDACTED]

6.19 Exploratory and Additional Analyses

Exploratory analyses will be presented by treatment group for the safety population. Tabulations and figures will be presented overall [REDACTED]

6.19.1 Magnetic Resonance-based Liver Imaging

MR-based liver imaging will be performed at screening and Week 12 (Parts 1, 2, and 3) and at Week 24 (Part 3 only).

Descriptive statistics for observed values at baseline and postbaseline visits will be provided, along with the change from baseline to each postbaseline visit, tabulated by treatment group for the following endpoints:

- Whole liver gadoxetate MRI relative enhancement (RE)

[REDACTED]

[REDACTED]

[REDACTED]

Controlled Quality Management Document

Sponsor: Pliant Therapeutics Inc.

Protocol Number: PLN-74809-PSC-203

STATISTICAL ANALYSIS PLAN

Confidentiality Statement

This document [REDACTED] may not be duplicated, copied, altered or removed from company
without prior approval [REDACTED].

Controlled Quality Management Document

Sponsor: Pliant Therapeutics Inc.

Protocol Number: PLN-74809-PSC-203

STATISTICAL ANALYSIS PLAN

- Bile duct gadoxetate MRI time of arrival (unit: seconds)

■

A comparison of each parameter (PLN-74809 vs. placebo) will be performed. P-values will be derived from t-tests using the following SAS code:

■
■
■
■
■

The comparison will be analyzed between each treatment and placebo for the observed values and change from baseline values at each visit.

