2.3 Exploratory Objectives

The exploratory objectives of this study are as follows:

- To assess changes from baseline in liver fibrosis biomarkers, [REDACTED] PRO-C3 and Enhanced Liver Fibrosis (ELF) score
- To assess changes from baseline in alkaline phosphatase (ALP)
- To assess changes from baseline in magnetic resonance (MR)-based liver imaging
- To assess changes from baseline in patient-reported outcomes (PROs)

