6.19.2 Patient-Reported Outcomes

Questionnaires to assess PROs will be administered at baseline, Weeks 4 and 12 (Parts 1, 2, and 3), and at Week 24 (Part 3 only).

Descriptive statistics for observed values at baseline and postbaseline visits will be provided, along with the change from baseline to each postbaseline visit, tabulated by treatment group.

A comparison of each parameter change from baseline (PLN-74809 vs. placebo) will be performed. P-values will be derived from t-tests.

Tabulations and graphical summaries will be provided for the following PROs and associated subdomains (as appropriate):

- Partial Mayo Score for IBD

■
■
■

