6.19.3 Ultrasound-based Transient Elastography (FibroScan®)

Each participant will undergo an ultrasound-based transient elastography (FibroScan®) assessment at screening and Week 12 (Parts 1, 2, and 3) and at Week 24 (Part 3 only).

Confidentiality StatementThis document [REDACTED]
without prior approval [REDACTED]

may not be duplicated, copied, altered or removed from company [REDACTED].

Controlled Quality Management Document	
Sponsor:	Pliant Therapeutics Inc.
Protocol Number:	PLN-74809-PSC-203

STATISTICAL ANALYSIS PLAN

Descriptive statistics for observed values at baseline and postbaseline visits will be provided, along with the change from baseline to each postbaseline visit, tabulated by treatment group.

A comparison of each parameter (PLN-74809 vs. placebo) will be performed. P-values will be derived from t-tests.

[REDACTED]

[REDACTED]

Safety Analyses

Safety analyses will be presented by the treatment received for the Safety Population.

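### MR imaging, PRO and FibroScan comparisons are t-tests without baseline adjustment, and MR is tested on two scales with no statement of which governs

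*SAP*

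**What the plan says.** **MR (6.19.1).** Imaging is done at screening, at Week 12 in all Parts and at Week 24 in Part 3. "P-values will be derived from t-tests using the following SAS code"; the code itself is redacted. Then: "The comparison will be analyzed between each treatment and placebo for the observed values and change from baseline values at each visit". Section 2.3 gives the objective as "To assess changes from baseline in magnetic resonance (MR)-based liver imaging".

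**PROs (6.19.2).** "A comparison of each parameter change from baseline (PLN-74809 vs. placebo) will be performed. P-values will be derived from t-tests". The visits are Weeks 4 and 12, plus Week 24 in Part 3. The one PRO named in the visible text is the partial Mayo score, which Section 6.12 describes as a baseline characteristic of participants with ongoing inflammatory bowel disease (IBD).

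**FibroScan (6.19.3).** "A comparison of each parameter (PLN-74809 vs. placebo) will be performed. P-values will be derived from t-tests". Whether observed values or changes are tested is not visible, and redacted lines follow.

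**Biomarkers (6.18.1, 6.18.2).** ANCOVA is used with one post-baseline visit and MMRM with two or more. Both report LS mean difference, standard error, 95% CI and p-value for each dose against pooled placebo. The model terms are redacted.

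**Tier and design.** Section 3.4 lists biomarkers, MR and PROs together as exploratory endpoints; Section 3.5 lists FibroScan as additional. Section 5 stratifies randomization by UDCA use and allocates 21 active and 7 placebo per dose. Section 6.11 pools placebo across Parts.

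**The concern.** A two-sample t-test has no place for a covariate. Baseline is measured for all three endpoint families, and the plan already uses models that can adjust for it on biomarkers of the same tier as MR and PROs. The visible text gives no reason for the simpler method.

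The MR section has a second problem. Two p-values answer each question, one on the scale of the objective and one not, and no rule says which to rely on. The observed-value test leaves all between-participant baseline variation in the error. The change test removes baseline with a slope fixed at 1, so it over-corrects a chance imbalance when the true slope is lower.

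At stake is the width of the intervals in small groups, and the chance that the MR report offers two conflicting answers. No decision rule is at stake, because the visible SAP sets no significance level or success criterion for these endpoints.

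**Working it through.** **Inputs from the SAP.** Section 5: 4 x (21 + 7) = 112, which reproduces the stated total. Pooled placebo is 4 x 7 = 28. Week 12 comparisons are therefore 21 vs 28. Week 24 exists only in Part 3, so it is 21 vs 7. The SAP states no power calculation for these endpoints.

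**Assumptions.** The SAP gives no baseline/follow-up correlation r, so 0.5, 0.7 and 0.9 are shown. Further assumptions are equal SDs at both times, no dropout and, at Week 12, placebo exchangeable across Parts.

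**Variance per observation, in units of the outcome variance.** Observed value: 1. Change: 2(1 - r). ANCOVA: 1 - r².

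**Cost of covariates.** With q covariates, g groups and N participants, the ANCOVA variance is multiplied by 1 + q/(N - g - q - 1). For q = 2 (baseline and UDCA):
- Week 12, one model: 1 + 2/(112 - 5 - 2 - 1) = 1 + 2/104 = 1.019
- Week 24, Part 3: 1 + 2/(28 - 2 - 2 - 1) = 1 + 2/23 = 1.087

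**Net variance saving.** Against change: 1 - factor x (1 + r)/2. Against observed: 1 - factor x (1 - r²). Example at r = 0.7, Week 12: 1 - 1.019 x 0.85 = 13.4%, and 1 - 1.019 x 0.51 = 48.0%.

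| | r = 0.5 | r = 0.7 | r = 0.9 |
|---|---|---|---|
| Week 12, vs change | 23.6% | 13.4% | 3.2% |
| Week 12, vs observed | 23.6% | 48.0% | 80.6% |
| Week 24, vs change | 18.5% | 7.6% | -3.3% |
| Week 24, vs observed | 18.5% | 44.6% | 79.3% |

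A simulation of 12,000 trials per setting, with UDCA unrelated to outcome, gave savings against change of 23.3/14.3/3.0% at Week 12 and 17.8/7.4/-3.8% at Week 24, in line with the formulas.

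**95% CI half-widths at r = 0.7, in SD.** t x sqrt(1/n1 + 1/n2) x sqrt(variance), with the cost factor included for ANCOVA and a pooled-variance t-test assumed.
- Week 12 (47 df for the t-tests, 105 for ANCOVA): observed 0.58, change 0.45, ANCOVA 0.41.
- Week 24 (26 and 24 df): 0.90, 0.69, 0.67.

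**Chance imbalance.** One SD of the baseline difference at 21 vs 28 is sqrt(1/21 + 1/28) = 0.289 SD. It shifts the change estimate by (1 - r) x 0.289 = 0.14/0.09/0.03 SD and the observed-value estimate by r x 0.289 = 0.14/0.20/0.26 SD.

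**Two MR scales.** Four doses at Week 12 plus 320 mg at Week 24 make 5 comparisons, so two scales give 10 p-values per parameter. In 40,000 simulated null trials per setting (r = 0.5 to 0.9, two-sided 0.05 assumed), each test alone kept about 5%. At least one of the pair was significant in about 9.0 to 9.5%, and the two disagreed in about 8 to 9%.

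**Partial Mayo score.** If it is analysed only in participants with IBD, and 50 to 70% of the 28 in Part 3 have IBD (assumed), N is about 14 to 20 and the factor 1 + 2/(N - 5) is 1.22 to 1.13. Against change at Week 24, the adjusted variance is then between 4% worse (1.22 x 0.85 = 1.04) and 4% better (1.13 x 0.85 = 0.96) at r = 0.7, and 10 to 2% worse at r = 0.8. With baseline as the only covariate the factor is 1 + 1/(N - 4) = 1.10 to 1.06, a gain of 6 to 10% at r = 0.7 and 1 to 4% at r = 0.8.

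**The case against.** The best defence is that a t-test on change is valid under randomization, uses baseline and answers the stated objective. On that view the PRO plan and the MR change test contain no error, only a choice. This stands: the case against them is precision and consistency, and where r is near 0.9 the gain is 3% of variance at Week 12 and a small loss at Week 24. The MR objective is also answered, since the change test is planned. The observed-value test can moreover keep participants without a baseline value, though a descriptive summary keeps them too.

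The count of 10 p-values is one reading. Section 6.8.5 adds an all-doses column, Section 7 repeats analyses at the interims, and some MR parameters are redacted. The duplication of scales does not depend on the count.

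Three stronger readings are tempting, and the SAP supports none of them:
- **That biomarkers are adjusted for UDCA and these endpoints are not.** The biomarker model terms are redacted, so the contrast cannot be shown. The calculations also treat UDCA as unrelated to outcome, so it enters only as a cost.
- **That the change t-test is biased or inflates type I error.** It keeps its level, and no decision rule hangs on the MR pair.
- **That FibroScan is tested on the wrong scale.** The quantity tested is not visible, and its tier is additional.

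**Conclusion.** The point holds as one of precision and clarity. The clearest part is MR: observed values receive p-values beside change, although change is the objective and nothing visible ranks the two. At r = 0.7 and Week 12 the observed-value test has nearly twice the variance of ANCOVA net of covariate cost (1/0.52). The change test loses much less, and its loss shrinks as r rises.

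The sizes rest on assumed correlations, equal SDs and full planned numbers. The Week 12 figures also need placebo to be exchangeable across Parts; the Week 24 figures, within Part 3, do not. None of them applies to the partial Mayo score if it is restricted to participants with IBD, where adjustment at Week 24 may bring no gain or a small loss.

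Importance is minor. MR and PROs are exploratory, FibroScan is additional, and the primary safety conclusion is untouched. The edit is worth making because it is cheap.

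**What to change.** - **6.19.1:** make change from baseline the only MR scale with a p-value, and keep observed values descriptive.
- **6.19.1 to 6.19.3:** replace the t-tests with the model class of Section 6.18, adjusted for the baseline value: ANCOVA, or MMRM where visits repeat. Report the LS mean difference, standard error and 95% CI for each dose.
- **UDCA:** add the stratum as a term to respect the stratified randomization. No precision gain is claimed for it.
- **Week 24:** compare 320 mg with Part 3 placebo and state n. For the partial Mayo score at this visit, the change t-test or a model with baseline as the only covariate may be kept.

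The cost is one SAP edit and a change of SAS procedure; baseline values and UDCA use are already collected. One or two degrees of freedom are spent, which is noticeable only at Week 24. Participants without a baseline value are lost, as they already are from the change test. If the edit follows the Part 1/2 unblinding, the SAP addendum foreseen in Section 6 should label it as made after those results were available.

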6.19.2 Patient-Reported Outcomes

Questionnaires to assess PROs will be administered at baseline, Weeks 4 and 12 (Parts 1, 2, and 3), and at Week 24 (Part 3 only).

Descriptive statistics for observed values at baseline and postbaseline visits will be provided, along with the change from baseline to each postbaseline visit, tabulated by treatment group.

A comparison of each parameter change from baseline (PLN-74809 vs. placebo) will be performed. P-values will be derived from t-tests.

Tabulations and graphical summaries will be provided for the following PROs and associated subdomains (as appropriate):

- Partial Mayo Score for IBD

■
■
■

6.19.3 Ultrasound-based Transient Elastography (FibroScan®)

Each participant will undergo an ultrasound-based transient elastography (FibroScan®) assessment at screening and Week 12 (Parts 1, 2, and 3) and at Week 24 (Part 3 only).

Confidentiality StatementThis document [REDACTED]
without prior approval [REDACTED]

may not be duplicated, copied, altered or removed from company [REDACTED].

Controlled Quality Management Document	
Sponsor:	Pliant Therapeutics Inc.
Protocol Number:	PLN-74809-PSC-203

STATISTICAL ANALYSIS PLAN

Descriptive statistics for observed values at baseline and postbaseline visits will be provided, along with the change from baseline to each postbaseline visit, tabulated by treatment group.

A comparison of each parameter (PLN-74809 vs. placebo) will be performed. P-values will be derived from t-tests.

[REDACTED]

[REDACTED]

Safety Analyses

Safety analyses will be presented by the treatment received for the Safety Population.

6.20 Adverse Events

AE analyses will be presented by the actual treatment received for the Safety Population.

[REDACTED]

AEs will be collected from the time of informed consent through completion of the participant's last study visit.

A treatment-emergent adverse event (TEAE) is defined as:

- Any AE that has an onset on or after the first dose of study drug through completion of the last study visit.
- Any pre-existing AE that has worsened in severity on or after the first dose of study drug through completion of the last study visit.

AEs occurring prior to first dose of study drug are considered non-treatment emergent and will be listed only.

The Investigator will determine the relationship of the AE to treatment (related, not related). If an AE has missing relationship it is assumed to be related to the study drug for analysis purposes.

Severity of the AE will be graded using the Common Terminology Criteria for Adverse Events (CTCAE) grading system (Version 5.0): Grade 1 (mild), Grade 2 (moderate), Grade 3 (severe), Grade 4 (life-threatening), Grade 5 (fatal). Grade 3 (severe) will be assumed for an AE with missing grade.

An overall summary of AEs (number of participants with an event) will be presented by treatment group and overall, for the following:

- TEAE

[REDACTED]

[REDACTED]

Controlled Quality Management Document

Sponsor: Pliant Therapeutics Inc.

Protocol Number: PLN-74809-PSC-203

STATISTICAL ANALYSIS PLAN

Confidentiality Statement

This document [REDACTED] may not be duplicated, copied, altered or removed from company
without prior approval [REDACTED].

Controlled Quality Management Document

Sponsor:

Pliant Therapeutics Inc.

Protocol Number:

PLN-74809-PSC-203

STATISTICAL ANALYSIS PLAN

- TEAE related to study drug
- TEAE Related to a Study Procedure
- Serious TEAE
- Serious TEAE Related to Study Drug
- TEAE of CTCAE Grade 3 or Higher
- TEAE of CTCAE Grade 3 or Higher Related to Study Drug
- TEAE Leading to Interruption of Study Drug
- TEAE Leading to Withdrawal of Study Drug
- TEAE Leading to Early Termination from Study
- TEAE Leading to Death

Summaries of TEAEs (number of participants with an event) will be presented by system organ class and preferred term by treatment group for the following:

- TEAE
- TEAE Related to Study Drug
- Serious TEAE
- Serious TEAE Related to Study Drug
- TEAE Related to a Study Procedure
- TEAE of CTCAE Grade 3 or Higher
- TEAE of CTCAE Grade 3 or Higher Related to Study Drug
- TEAE Leading to Withdrawal of Study Drug
- TEAE by SOC, PT and Maximum Grade (incidence only)
- [REDACTED]

The following listings of TEAEs will be presented in Section 14.3.2 of the CSR.

- TEAE Leading to Withdrawal of Study Drug
- TEAE Leading to Early Termination from Study
- TEAE Leading to Death
- Serious TEAE

System organ class will be presented in descending order of frequency in the pooled PLN-74809 group and then alphabetically. Preferred terms will be displayed in descending order of frequency in the pooled PLN-74809 group and then alphabetically.

Confidentiality StatementThis document [REDACTED]
without prior approval [REDACTED]

may not be duplicated, copied, altered or removed from company [REDACTED]

Controlled Quality Management Document

Sponsor:

[figure not shown]
Pliant Therapeutics Inc.

Protocol Number:

PLN-74809-PSC-203

STATISTICAL ANALYSIS PLAN

For summary by severity, participants reporting more than one AE per system organ class and preferred term will only be counted once for the most severe event.

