1 INTRODUCTION

This document details the planned statistical analyses for Pliant Therapeutics Inc. Study PLN-74809-PSC-203, “A randomized, double-blind, dose-ranging, placebo-controlled, Phase 2a evaluation of the safety, tolerability, and pharmacokinetics of PLN-74809 in participants with primary sclerosing cholangitis (PSC) and suspected liver fibrosis (INTEGRIS-PSC)”.

The proposed analyses are based on the contents of the [REDACTED]

[REDACTED]

This is a Phase 2a, multicenter, 3-part, randomized, double-blind, dose-ranging, placebo-controlled study to evaluate the safety, tolerability, and PK of once-daily (QD) treatment with PLN-74809 in male and female participants aged 18 to 75 years with an established diagnosis of large duct PSC and suspected liver fibrosis. Part 1 will evaluate 40 mg PLN-74809 and placebo, Part 2 will evaluate 80 and 160 mg PLN-74809 and placebo and Part 3 will evaluate 320 mg PLN-74809 and placebo. Placebo participants will be pooled across the study when comparing to PLN-74809 treatment groups.

Each study part will include an up to 42-day screening period, followed by a treatment period of either 12 weeks (Parts 1 and 2) or at least 24 weeks and up to 48 weeks (Part 3), and finally a 4-week post-treatment follow-up period. Based on regulatory considerations, randomization to dose level in Part 2 of the protocol (80 or 160 mg PLN-74809) was conducted in either parallel or sequential manner.

Each participant in Parts 1 and 2 will participate in the study for approximately 154 days (22 weeks), including screening, treatment, and post-treatment safety follow-up. The duration for Part 3 of the study will be variable depending on the study enrollment rate. The duration of participation will be approximately 238 days (34 weeks) for the last participant enrolled and approximately 406 days (58 weeks) for the first participant enrolled including screening, treatment, and post-treatment safety follow-up. The end of Part 3 will commence once the last participant reaches 24 weeks of treatment. At that time, all study participants will complete their next scheduled visit (End of Treatment [EOT]) and the 4 weeks of follow up (End of Study [EOS]). The end of study is defined as the last visit of the last participating participant.

Confidentiality Statement

This document [REDACTED] may not be duplicated, copied, altered or removed from company [REDACTED]
without prior approval [REDACTED]

	Controlled Quality Management Document	

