3 ENDPOINTS

3.1 Primary Safety Endpoint

The primary safety endpoint is the incidence of treatment-emergent adverse events (TEAEs).

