5 RANDOMIZATION

For each planned PLN-74809 dose in each Part of the study, n=21 subjects will be randomized to PLN-74809 and n=7 participants will be randomized to placebo for a total of n=28 and in total, N=112 for 4 PLN-74809 doses (40, 80, 160 and 320 mg).

Approximately 112 participants may be enrolled in this study (28 participants in Part 1, 56 participants in Part 2, and 28 participants in Part 3).

Part 1: 28 eligible participants will be randomized in a 3:1 ratio (40 mg PLN-74809:placebo).

Part 2: 28 eligible participants per cohort (56 in total) will be randomized in a 3:1 ratio (PLN-74809:placebo). PLN-74809 doses administered in each cohort will be 80 mg or 160 mg.

Part 3: 28 eligible participants will be randomized in a 3:1 ratio (320 mg PLN-74809:placebo).

Randomization will be stratified by use of ursodeoxycholic acid (UDCA) (yes/no).

Confidentiality Statement

This document [REDACTED]
without prior approval [REDACTED]

may not be duplicated, copied, altered or removed from company [REDACTED].

	Controlled Quality Management Document	
	Sponsor:	Pliant Therapeutics Inc.
	Protocol Number:	PLN-74809-PSC-203
STATISTICAL ANALYSIS PLAN		

Participants will be centrally randomized at the baseline visit using an interactive response technology (IRT) system, according to a computer-generated randomization scheme. Randomization will occur immediately prior to the first dose (Day 1).

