6.8.3 Summary Statistics

Continuous variables will be summarized using an 8-point summary, the number of non-missing observations, mean, standard deviation, median, interquartile range (Q1, Q3), minimum (min), and maximum (max).

PK concentration data will be summarized using a 11-point summary, the number of non-missing observations (n), arithmetic mean (mean), standard deviation (SD), geometric mean, median, interquartile range (Q1, Q3), minimum (min), maximum (max), coefficient of variation (CV%) and geometric CV%

Categorical variables will be summarized by presenting the frequency and percent. Percentages will be based on the number of non-missing observations or the count in the participant population, unless otherwise specified. For each variable, all categories will be shown. Zero frequencies (but not the percent) within a category will be presented.

Incidence of AEs, medical history, and concomitant medications will be reported at the participant level. Participants can only be counted once within each preferred term and system organ class under the highest severity and relationship to study drug. Percentages will be calculated using the number of participants in the treatment group for the Safety Population.

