6.8.5 Data Displays

All TFLs will be generated as individual Rich Text Format (.rtf) files using SAS [REDACTED]. Data summaries and graphical analyses will be reported within Section 14 of the CSR and individual participant data listings within Appendix 16.2 of the CSR.

Confidentiality Statement	
This document [REDACTED] without prior approval [REDACTED]	may not be duplicated, copied, altered or removed from company [REDACTED]

	Controlled Quality Management Document	
	Sponsor:	Pliant Therapeutics Inc.
	Protocol Number:	PLN-74809-PSC-203

STATISTICAL ANALYSIS PLAN

Participant disposition, baseline characteristics, and demographics, will be presented by treatment group (including all PLN-74809) and overall. Other summaries will be presented by treatment group (including all PLN-74809) only.

Treatment group labels will be displayed as follows:

PLN-74809 40 mg (N=XX)	PLN-74809 80 mg (N=XX)	PLN-74809 160 mg (N=XX)	PLN-74809 320 mg (N=XX)	All PLN-74809 (N=XX)	Placebo (N=XX)
------------------------------	------------------------------	-------------------------------	-------------------------------	----------------------------	-------------------

Listings will be sorted in the following order, study part (Parts 1, 2, and 3), treatment group, participant number, parameter, and visit unless otherwise stated. All data for randomized participants will be listed.

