6.11 Pooled Placebo

Participants in the placebo group will be pooled across study Parts for summaries and comparison to PLN-74809 treatment groups.

--	--

Controlled Quality Management Document

Sponsor:	Pliant Therapeutics Inc.
----------	--------------------------

Protocol Number:	PLN-74809-PSC-203
------------------	-------------------

STATISTICAL ANALYSIS PLAN**Confidentiality Statement**

This document [REDACTED] may not be duplicated, copied, altered or removed from company [REDACTED] without prior approval [REDACTED].

Controlled Quality Management Document

Sponsor:

Pliant Therapeutics Inc.

Protocol Number:

PLN-74809-PSC-203

STATISTICAL ANALYSIS PLAN**6.12 Baseline and Clinical Characteristics**

Baseline summaries will be presented by treatment group (PLN-74809 dose (40, 80, 160 or 320 mg, All PLN-74809) or Placebo) and overall (PLN-74809 dose and Placebo) for the following variables based on the safety population:

Demographic Data

- Age at informed consent (years)
- Sex
- Ethnicity
- Race, where more than 1 race is selected the participant will be presented under the 'Multiple races' category in the summary but each selected race will be displayed in the listing.

Baseline Characteristics

- Weight at Screening (kg)
- Height at Screening (cm)
- BMI at Screening (kg/m²)
- Fertility status (childbearing potential, postmenopausal, surgically sterile)

Clinical Characteristics

- Duration since diagnosis at baseline (defined as the number of months from start date of first date reported for medical history preferred term "Cholangitis sclerosing" to first dose)
- Use of UDCA (Yes/no)
- Duration of UDCA usage at baseline (defined as the number of months from start date of UDCA to first dose)
- Partial Mayo Score for IBD (for participants with IBD ongoing at screening)

■ [REDACTED]

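### Crude TEAE incidence is counted over 16 weeks for 40, 80 and 160 mg, 28 to 52 weeks for 320 mg and 19 to 25 weeks on average for pooled placebo, so the final by-dose comparisons are biased

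*SAP*

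**What the plan says.** Section 3.1 sets the endpoint: "The primary safety endpoint is the incidence of treatment-emergent adverse events (TEAEs". Section 6.20 defines a TEAE as "Any AE that has an onset on or after the first dose of study drug through completion of the last study visit", so the post-treatment follow-up is included. A second limb, for worsening of a pre-existing AE, runs to the same visit.

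Section 6.8.3 gives the denominator: "Percentages will be calculated using the number of participants in the treatment group for the Safety Population".

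Section 1 describes "a treatment period of either 12 weeks (Parts 1 and 2) or at least 24 weeks and up to 48 weeks (Part 3", each followed by 4 weeks of follow-up. Total participation in Part 3 is "approximately 238 days (34 weeks) for the last participant enrolled and approximately 406 days (58 weeks) for the first participant enrolled". Only Part 3 gives 320 mg.

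Section 5 states that for each dose "n=21 subjects will be randomized to PLN-74809 and n=7 participants will be randomized to placebo". Section 6.11 adds: "Participants in the placebo group will be pooled across study Parts for summaries and comparison to PLN-74809 treatment groups". Section 6.8.5 shows one placebo column and says: "Other summaries will be presented by treatment group (including all PLN-74809) only".

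Section 7 stops AE counting at about Week 12 for the Part 3 interim only. Later events go into the final analysis. The readable text has no common-window TEAE table, no rate per unit of follow-up time and no TEAE summary by Part.

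**The concern.** A crude percentage of participants with an event rises with the time they are watched. Here that time is set by the Part, and the dose is tied to the Part. The top dose is watched longest and the three lower doses shortest. The placebo column mixes both kinds of Part, three quarters short and one quarter long. Each dose is then read against a placebo group observed for a different time, with the error in opposite directions for 320 mg and the lower doses.

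Safety and tolerability are the primary objective of this dose-ranging trial. A pattern produced by follow-up time could be read as a dose-safety gradient. The visible AE tables carry no test, so the harm is a misleading description, not an inflated type I error. The same applies by dose to the serious, Grade 3 or higher, related and withdrawal TEAE tables, and to the incidence of treatment-emergent laboratory abnormalities in Section 6.20.2.

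**Working it through.** **The plan's own durations (Section 1).** Screening of 42 days, plus treatment of 84, 168 or 336 days, plus follow-up of 28 days, gives 154, 238 and 406 days (22, 34 and 58 weeks). All three match the SAP.

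**TEAE windows.** Removing the 6 weeks of screening:

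- 40, 80 and 160 mg: 22 − 6 = 16 weeks.
- 320 mg: 34 − 6 = 28 weeks (last enrolled) to 58 − 6 = 52 weeks (first enrolled).
- Pooled placebo (21 participants from Parts 1 and 2, 7 from Part 3): mean (21 × 16 + 7 × w)/28 = 19, 22 and 25 weeks for a mean Part 3 window w of 28, 40 and 52.
- All PLN-74809: (63 × 16 + 21 × w)/84 = 19, 22 and 25 weeks. This equals placebo, so that column is balanced.

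**Expected incidence with no drug effect.** The SAP gives no event rate, so the following is assumed: the same constant hazard in every group, full follow-up, and incidence p16 by Week 16. Then:

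- 320 mg: p(w) = 1 − (1 − p16)^(w/16)
- pooled placebo: 0.75 × p16 + 0.25 × p(w)
- lower doses: p16

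For w = 28 and p16 = 10%: p(28) = 1 − 0.9^1.75 = 16.8%; placebo = 7.5% + 0.25 × 16.8% = 11.7%; ratio 1.44.

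| p16 = 10%, Part 3 window | 320 mg | Placebo | 320 mg / placebo | Lower doses / placebo |
|---|---|---|---|---|
| All at 28 weeks | 16.8% | 11.7% | 1.44 | 0.85 |
| Even spread over 28–52 weeks (mean 40) | 23.1% | 13.3% | 1.74 | 0.75 |
| All at 52 weeks (upper bound) | 29.0% | 14.7% | 1.97 | 0.68 |

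All PLN-74809 in the even-spread row is also 13.3%.

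**Higher incidence, even spread.** At p16 = 60%, 320 mg shows 89.1%, placebo 67.3% and the lower doses 60%. At p16 = 90% the 320 mg excess is 6.2, 7.3 and 7.5 points for windows of 28, 40 and 52 weeks.

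**Chance of an apparent excess.** Exact binomial, p16 = 10%, 21 participants on 320 mg against 21 + 7 on placebo. The probability that 320 mg exceeds placebo by at least 10 points is 31%, 48% and 63% at 28, 40 and 52 weeks. If all placebo participants had the same window as 320 mg it would be 17%, 20% and 22%.

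**Early clustering.** Hazard after Week 12 equal to f times the earlier hazard, p16 held at 10%, even spread:

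| f | 320 mg | Placebo | Ratio |
|---|---|---|---|
| 1 | 23.1% | 13.3% | 1.74 |
| 0.5 | 17.7% | 11.9% | 1.49 |
| 0.25 | 14.3% | 11.1% | 1.29 |
| 0 | 10.0% | 10.0% | 1.00 |

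**The case against.** **The interims already give nearly equal windows.** The Parts 1 and 2 interim compares 40, 80 and 160 mg with their own placebo over the same time, and the Part 3 interim stops at about Week 12. This is a real mitigation. But Section 7 does not carry the cut into the final tables. If the Part 3 interim counts Parts 1 and 2 events to Week 16, it would tilt the other way; the redacted cut-off leaves that open.

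**Redactions may hide a remedy.** Text is missing in Section 6.20 and Section 9, and the list of tables cannot be read. So it cannot be shown that no adjusted table exists. The windows, the crude denominator and the pooling rule are nevertheless all in readable text, and the fix is conditional.

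**The tables are descriptive, and exposure is shown.** Section 6.15 summarizes duration of exposure, so a careful reader could see the imbalance. That corrects no percentage, and Section 6.11 says that pooling is for comparison.

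**The size is assumed.** This stands. At 60% by Week 16 the 320 mg ratio is 89.1/67.3 = 1.32. The primary endpoint, any TEAE, may well be common, so the 10% case fits less common categories better.

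**Even accrual ignores the next-visit rule.** Section 1 has participants finish treatment at their next scheduled visit once the last one reaches Week 24. With the visible visits at Weeks 32, 40 and 48, equally likely, the windows become 36, 44 and 52 weeks. At 10% this gives 25.1% against 13.8%, ratio 1.82. That is inside the range above and adds to the bias.

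**Laboratory data are mostly time-matched.** This is correct for the by-visit summaries and shift tables. Only the incidence of treatment-emergent abnormalities is affected.

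**Conclusion.** The concern holds for the final by-dose comparisons. The windows follow exactly from the SAP, at full enrollment and full follow-up. The direction needs only that some first events start after Week 16. The size rests on assumed incidence and hazard shape. At 10% by Week 16 with a constant hazard, the 320 mg ratio to placebo under no drug effect is 1.44 to 1.97, and that of the lower doses 0.85 to 0.68. It shrinks as incidence nears 100% or as events cluster early. The 52-week end is an upper bound, because only the earliest enrolled can reach it, and dropout shortens every window.

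The All PLN-74809 column and the Parts 1 and 2 interim are not affected. This should be fixed before the final analysis.

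**What to change.** Unless a redacted table already does this, add by SAP addendum, as Section 6 allows:

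1. Make the main by-dose comparison with pooled placebo on onset from Day 1 to Week 12 in all Parts, for TEAEs and for treatment-emergent laboratory abnormalities. Use the same window for every group at the Part 3 interim. Week 12 is the longest window with all groups on treatment, because Week 16 is off treatment in Parts 1 and 2 (Section 6.18, Table 1).
2. For full follow-up, report participants with an event per 100 participant-years for each TEAE category, with time at risk from first dose to first event or last study visit. The Section 6.2.6 duration should not be the denominator: it ends at last dose, while TEAEs count through follow-up. The mismatch would differ by Part: 16/12 = 1.33 in Parts 1 and 2 against 40/36 = 1.11 for a 40-week Part 3 window.
3. Show Part 3 events after Week 12 descriptively, 320 mg beside the concurrent Part 3 placebo group, noting that it has 7 participants.

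The cost is an addendum and a few tables, with no new data. Later events move to separate tables, and the late Part 3 display will be very imprecise. Exposure-adjusted rates assume a roughly constant hazard and would favour 320 mg if events cluster early, so the common window should lead.
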